2.1 General Information

This document describes the UKLS trial and provides information about procedures for entering participants into it. The protocol should not be used as an aide-memoir or guide for the treatment of other patients. Every care was taken in its drafting, but corrections or amendments may be necessary. These will be circulated to the registered investigators in the trial. However, centres entering participants for the first time are advised to contact the coordinating centre (Cancer Research UK Liverpool Cancer Trials Unit (LCTU)) to confirm they have the most up to date version. Clinical problems relating to this trial should be referred to the relevant Chief Investigator via the LCTU.

2.2 Statement of Compliance

This study is designed to comply with the guideline developed by the International Conference on Harmonisation (ICH) for Good Clinical Practice (GCP) and will be conducted in compliance with the protocol, Research Governance Framework for Health and Safety Care and the LCTU Standard Operating Procedures (SOPs).

2.3 UK Registration

This study will have National Research Ethics Service (NRES) approval and each centre must undergo Site Specific Assessment (SSA) by the relevant Trust Research and Development (R&D) department and NHS sites must be granted R&D approval from each Trust where the trial will be carried out. In addition the trial will have approval from the National Information Governance Board for Health and Social Care for screening potential participants from the local PCT databases.

[figure not shown]
3 Protocol Summary

Title:	UK Lung Screening Trial (UKLS)
Design:	Randomised controlled screening trial
Sample Size:	Maximum 4,200 participants from the UK for the Pilot Trial Maximum 32,000 participants from the UK for the Main Trial.
Study Period:	Pilot: 14 months. Main Trial: 10 years
Main Inclusion Criteria:	
 1. Risk criteria based on the LLP Risk Prediction Model (includes age, sex, smoking duration, history of previous pneumonia, history of previous cancer, family history (early/ late onset) exposure to asbestos – algorithm 2. Males and females aged between 50 to 75 years old 3. Fully informed written consent given
Main Exclusion Criteria:	
 1. Unable to give consent 2. Co-morbidity which would unequivocally contra-indicate either screening or treatment if lung cancer were detected. 3. A CT scan of the chest performed within one year of the invitation to be screened. 4. Any condition precluding written informed consent 5. Inability to lie flat 6. Weight greater than 200 kg (too large for CT scanner)
Number of Sites:	
The pilot trial will have two participating centres:
 
 • Liverpool Heart and Chest Hospital • Papworth Hospital 
Both centres will predominately use their own fixed site CT. However, the feasibility of using mobile CT units will be trialled at 1 site for a 6 week period in the pilot
 
The main trial will take place at a further 5 sites still to be determined.
 
The Royal Brompton Hospital will act as a second reading centre for all the CT scans in the both the pilot and main trial.

Study Duration:	10 years
Description of Intervention:	Low dose Computed Tomography (CT) of the lungs
The objectives of the Pilot UKLS	
 1. Will the proposed method of recruitment (based on the protocol of a two-stage postal survey of risk directly


study:
	
aimed at the general population) deliver the required numbers? This entails estimating:
 
 a. Response rates to questionnaires. b. Proportion of subjects approached who are eligible. c. Proportion of eligible subjects who consent to randomisation. d. Proportion of subjects randomised to LDCT who comply with intervention. 
 2. How many subjects need to be approached to obtain the required full trial population? 3. Do the recruitment, randomisation and scanning protocols work in practice? Is the recruit's journey from initial survey to LDCT scanning logistically efficient? 4. Are both fixed and mobile CT units practicable for trial purposes - is one preferable to the other in terms of cost/convenience? 5. Testing of staff training programmes. 6. Testing of QA procedures, for radiology and technology, including radiation dose aspects. 7. Do questionnaires or consent/information procedures or documentation need revising? 8. Review recruitment in hard to reach groups 9. UKLS database capable of capturing all of the required information from the recruitment phase to CT screening, investigations and treatment. 10. Collection of blood *sputum specimens at the recruitment phase, and QC. 11. Provide Screening data for HTA review at Month 12 of the pilot for review and decision whether to fund the Main UKLS trial. 12. Management of UKLS through the LCTU

Main Study Primary Objectives:
	
 1. To establish the impact of pre-clinical detection of lung cancer mortality by comparing lung cancer mortality between the control group and the screened groups combined. 2. To establish if there is a lung cancer mortality benefit from CT screening 3. Establish total mortality benefit 4. Cost effectiveness of a national lung cancer screening programme.

Main Study Secondary Objectives:
	
 1. To determine the physical morbidity associated with lung cancer screening 2. To determine the resource implications of screening and the resulting intervention 3. To assess the feasibility of population screening for lung cancer as reflected by uptake of invitations and compliance rates with annual screening 4. Establish a blood and tissue bank for the future assessment of early detection diagnostics and novel

	tumour biomarkers
--	-------------------

Schematic UKLS Study Design:

4 Background Information

4.1 Introduction

Lung cancer kills more people worldwide than other malignancy. Currently 33,500 individuals die each year in the UK from lung cancer. The number of deaths has fallen in the past years and this is likely to be due to a decline in tobacco smoking, and possibly greater public awareness. However, there is now a large ex-smoking population in the USA and Europe, who remain at high risk of developing lung cancer, which is dependent on their smoking duration prior to tobacco cessation. This group of individuals now exceeds current smokers in both the USA and Europe and will continue to do so over the next two to three decades. Screening to detect the disease before patients develop any symptoms is a control measure urgently requiring evaluation as surgical resection at an early stage of the disease remains the only realistic option for a cure.

Chest radiography & sputum cytology lung cancer screening: The earliest lung screening trial was undertaken in London with over 55,000 individuals randomised to chest radiography every 6 months for three years or chest radiography at the beginning and end of the three year period [1]. No mortality difference was found between the two groups. Three major trials in the USA and one in Czechoslovakia were developed in the 1970's. The results of these large trials were disappointing as none of these studies showed any reduction in lung cancer mortality utilising chest radiography, with or without sputum cytology. One current trial which has 'usual care' only in the control arm is the lung component of the NCI PLCO (Prostate, Lung Colorectal & Ovarian) screening trial. In this trial, smokers are offered annual chest radiography for three years, and non-smokers two annual repeat screens; the results of this study are expected in 2010.

Low Dose CT lung cancer screening: Low dose computed tomography (LDCT) offers a major advance in imaging technology, which was introduced in the late 1990s [2]. This is more sensitive than chest radiography and has enabled detection of lung tumours smaller than one centimetre. Randomised trials of this technology as a screening tool have not as yet been completed. However, there have been a number of demonstration projects. Early studies of note include, the Early Lung Cancer Action Project (ELCAP) [3] in 1000 high-risk smokers; the Mayo Clinic project with 1520 individuals aged 50 years having annual sputum cytology and spiral CT screening [4], the Milan study [5] and a three-year mass screening programme using a mobile CT unit in Japan [6]. The ELCAP (observational) was later expanded to an international collaboration including 30,000 subjects.

The EU-US Spiral CT Collaboration was initiated in 2001 in Liverpool. Subsequent meetings throughout Europe resulted in the development of collaborative protocols which provided a mechanism for different trial groups to work together with the ultimate aim to pool results; the concept of which was formulated in the 'Liverpool Statement 2005'. [7]

The first major lung cancer RCT screening trial utilising LDCT was the National Lung Cancer Screening Trial (NLST), which is a combination of two trials, one set up by the US National Cancer Institute (NCI) and the other by the American College of Radiology Imaging Network (ACRIN). The NLST started in 2002 and completed enrolling in 2004. This study has over 50,000 former and current smokers randomised to annual LDCT or annual chest radiograph for three years. The major

objective of this was to determine whether LDCT reduces lung cancer mortality compared to a chest radiography arm. In November, 2010, the Director of the National Cancer Institute reported that the National Lung Screening Trial (NLST) showed that spiral CT screening when compared to chest X-ray evaluation resulted in a 20% reduction in lung cancer-related mortality. (<http://www.cancer.gov/newscenter/pressreleases/2010/NLSTresultsRelease>).

The NELSON RCT trial was launched in 2003 in the Netherlands and Belgium, [8] and now incorporates centres in Denmark. This trial is designed to compare lung cancer mortality in a group randomised to LDCT screening compared to a control group, without screening. A great deal of attention was focused on the selection of a high risk population to thus reduce the cost but retain the power of the study. Potential study participants were approached by letter with a questionnaire on their smoking exposure and whether they wished to be included in the trial. The questionnaire was initially sent to 335,441 men and women aged 50-75 years old. Based on this dataset the selection criteria were developed, depending on duration of smoking, duration of smoking cessation in ex-smokers, number of cigarettes smoked per day and the mean estimated expected lung cancer mortality rate. In this trial, LDCT screening takes place in years 1, 2 and 4, with 10 years of follow-up. The trial has 20,000 individuals, randomised in equal numbers to LDCT or 'usual care'. A number of small trials have been initiated, in anticipation of combination with partner studies, or a future meta-analysis. These include the ItaLung and Dante Trials in Italy [9, 10] and the French randomised pilot study, Depiscan, comparing LDCT and chest radiography recently reported its baseline findings [11].

The evidence required to justify (or rule out) the provision of screening as a service is a randomised controlled trial of LDCT screening with usual care as the control regimen and lung cancer mortality as the endpoint. To date, we do not have the results of any randomised trials which can provide adequate evidence to justify the instigation of a National Lung Cancer Screening Programme. The results of the NLST and NELSON studies are eagerly awaited. The unanswered question which remains in the UK is whether either of these studies will provide adequate information on their own to justify the implementation of a UK National Screening Programme. Although the combined US study is large and should have precise results, the use of an active screening regime in the control group may raise problems of interpretation. The NELSON study has adequate power for a substantial benefit in a high risk group, but a lower baseline lung cancer mortality or smaller benefit than anticipated may jeopardise a conclusive result.

The UK National Screening Committee has determined 22 criteria for the viability, effectiveness and appropriateness of a screening programme (http://www.nsc.nhs.uk/uk_nsc/uk_nsc_ind.htm) ; 20 of which are relevant to LDCT lung cancer screening. Black *et al.*, [12] have undertaken a systematic review of the literature in order to ascertain whether there was evidence for any clinical effectiveness utilising LDCT for lung cancer screening. This review was undertaken at the time when there was a paucity of real data and thus the conclusions were drawn from two small trials with very variable results. Not surprisingly, their conclusion stated that there was insufficient evidence at the time to support LDCT screening. This remains the case.

The objective of the RCTs is to assess whether LDCT screening and treatment of early lesions will decrease lung cancer mortality compared to a control group without screening. Additionally, a UK trial would aim to test the intervention against the

criteria outlined by the UK Screening Committee, especially those concerning cost effectiveness. A useful aid to cost-effectiveness is the ability to select a population at sufficiently high risk to give a substantial harvest of tumours in return for the screening activity. The group selected should also be of sufficiently high risk that the benefits of the screening will outweigh the likely harms.

It is important to measure the psychological impact of any new form of screening. A range of studies of different types of screening indicate that false positive and abnormal screening results are associated with short-term increases in anxiety and worry. Negative psychological effects are possible in lung cancer screening, although it is not known how sustainable these effects will be, or how they compare with adverse effects from other forms of cancer screening. The very act of participation in the lung screening trial may cause anxiety, as well as anxiety awaiting the outcome of the CT screen. In the case of individuals who require further tests due to suspicious nodules, there is the potential for further sustained anxiety.

A review of CT screening conducted for the Health Technology Assessment (HTA) Programme examined six recent economic evaluation models of CT screening, constructed by Japanese and US researchers [13]. The review concluded that these models provided an insufficient basis for assessing CT screening in the UK, for three reasons. Firstly, the quality of reporting was described as “poor” in all cases, a lack of transparency in reporting precluding any assessment of scientific plausibility. Secondly, all of the models had been driven by assumptions about, for example, lung cancer aetiology, disease progression, screening effectiveness, survival and the like, and most of these assumptions remained “uncorroborated” by evidence. The proliferation of assumptions generated very wide confidence intervals about the estimated cost effectiveness ratios. Finally, none of the published models had been populated with UK economic data. However, an evidence-based screening regimen potentially applicable to the UK has been modelled more recently, and the incremental cost effectiveness ratio of a single screen amongst a high-risk male population has been calculated. On the basis of reasoned speculations as to how test parameters and costs might behave under screening, the model generates cost effectiveness ratios well within the range of values currently considered acceptable in England [14].

4.2 Rationale

The objective of the UKLS trial is to assess whether LDCT screening and treatment of early lesions will decrease lung cancer mortality compared to a control group without screening. Additionally, a UK trial would aim to test the intervention against the criteria outlined by the UK Screening Committee, especially those concerning cost effectiveness. A useful aid to cost-effectiveness is the ability to select a population at sufficiently high risk to give a substantial harvest of tumours in return for the screening activity. The group selected should also be of sufficiently high risk that the benefits of the screening will outweigh the likely harms.

The most efficient way of controlling cost will be to screen only those individuals who are at high risk of developing the disease. There has been increasing interest in developing methods for individual risk prediction for lung cancer. Models have been developed for use within high risk groups [15], and for the general population [16], based mainly on age and smoking. The predictive accuracy of lung cancer risk models may be further improved by the addition of other epidemiological risk factors [17]. The Liverpool Lung Project (LLP) [18] has recently developed a method to calculate absolute risk of lung cancer over a defined period, based on age, sex,

smoking duration, family history of lung cancer, history of non-pulmonary malignant tumour, history of pneumonia and occupational exposure to asbestos [19]. The LLP risk questionnaire has been validated in the Harvard case control, then EUELC case control and the LLP cohort studies. The LLP risk model has distinctive strengths. Firstly, the predictor variables are all explicitly defined and can be readily assessed at the time of patient presentation and secondly, patients can be assigned to their appropriate risk class on the basis of information from the initial history alone.

The screening process confers potential harms as well as potential benefits. In a randomised trial and in any future national screening service, the screening would be provided only to those whose risk was sufficiently high that the likely benefits outweigh the likely harms.

4.3 Objectives

The overall aim of the trial is to provide data required for an informed decision about the introduction of population screening for lung cancer. This involves establishing the impact of screening on lung cancer mortality, determining the best screening strategy and assessing the physical and psychological consequences and the health economic implications of screening. A further objective is to create a resource for future improvements to screening strategies.

4.4 Potential Risks and Benefits

4.4.1 Potential Risks

Any screening programme has the potential to cause harm. Even if evidence for a beneficial effect of lung cancer screening is established, for any one individual it is always possible that more harm than good will result from participation; for example, a cancer may be detected which was not destined to cause harm and investigations and treatments offered may produce serious side effects or even death.

1) The very act of participation in the lung screening trial may cause anxiety, as well as anxiety awaiting the outcome of the CT screen. In the case of individuals who require follow-up CT screens, there is the potential for further anxiety. In order to reduce this anxiety, we will provide an informative Participant Information Booklet, further information on our UKLS web site and also provide a telephone number for anxious patients to call at their "Pilot Site". The UKLS utilises a Research Nurse for recruitment for morning sessions, however the Research Nurse will be available each afternoon session to answer calls or make appointments to see anxious patients. If a patient is extremely anxious the Respiratory Consultant associated with the Pilot CT screening Trial Site, will provide an appointment to see these individuals. In such cases we will also inform the recruit's GP of their concerns, in order that they may have further support.

2) Adverse psychological consequences of screening: It is important to measure the psychological impact of any new form of screening. Our group has extensive experience in defining and measuring such harmful effects; the proposed pilot will provide the opportunity to test a draft measurement instrument. Negative psychological effects are possible in lung cancer screening, although it is not known how sustainable these effects will be, and how they compare with adverse effects from other forms of screening. Hence, ideally invitees should be fully informed of this risk, and receive adequate information on interpreting screening results. These considerations have shaped our draft invitation materials for the UKLS pilot.

3) Recruits may be concerned about the exposure to radiation from a CT scan. The amount of radiation delivered by one low dose CT scan of the chest to a standard-sized adult is approximately 1 mSv (in clinical practice a routine chest CT examination may be up to 10 mSv). 1 mSv is approximately equivalent to 5 months' worth of natural background radiation. The International Committee on Radiological Protection advises that there may be a small chance that low amounts of radiation may cause cell damage that will manifest itself as cancer many years after the exposure. In the UKLS protocol the radiation dose will almost invariably be less than 1 mSv. According to the Twelfth COMARE deliberations there is no threshold below which there is no deleterious effect from radiation. The risk of cancer induction for one low dose CT scan (UKLS protocol) is estimated at 1 in 20,000 for a healthy 50-year-old (this is additional to the lifetime likelihood of developing cancer of approximately 1 in 4). We will make the above information clear to all potential participants during the consent process.

4) Diagnostic workup may cause anxiety in recruits: Diagnostic work-up of patients with suspicious nodules may include bronchoscopies, biopsies, staging CT with contrast, PET scan, and surgical resection. The great majority of suspicious nodules will not grow and will be regarded as benign. This will be made clear to subjects recalled for additional investigation. The detection of such nodules is an unavoidable part of the screening programme. The Participant Information Booklet will provide a detailed explanation of why follow-up CT is needed in a relatively high proportion of subjects and associated risks. Modelling based on preliminary results from other screening trials has indicated that clinical work-up will only occur in a very small proportion of the CT screened population (estimated at 1.5% of which 70% will have lung cancer). The proportion of subjects that undergo these tests is kept low by application of the UKLS care pathway that ensures subjects are filtered by less invasive tests (repeat CT) until the probability of malignancy is sufficiently high to warrant invasive tests or resection. This requires strict adherence to the CT screening protocol and the rigorous training of the radiologists and radiographers.

5) Overdiagnosis: This is a major issue of any screening trial and can only be assessed in the Main UKLS Trial. The main outcome measure of overall, all-cause mortality will not be influenced by this bias. The pilot will have insufficient power to detect differences in mortality as a result of screening and therefore this bias will only be compensated for in the main trial.

6) Treatments: A significant increase in lung cancer diagnosis and treatment through screening inevitably leads to treatment complications and costs. Lung cancer resection carries a significant complication and mortality rate, influenced by a range of patient characteristics and co-morbidities. A feature of lung cancer surgical treatments is their ongoing capacity to compromise quality of life. Accordingly, the pilot will provide an opportunity to develop and test clinical monitoring forms for all treatments provided to patients with screen-detected cancers – and to examine the associated organisational and training issues.

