7.2 Exclusion Criteria

1. Unable to give consent
2. Co morbidity which would unequivocally contraindicate either screening or treatment if lung cancer were detected
3. A CT scan of the chest performed within one year of the invitation to be screened
4. Any condition precluding written informed consent
5. Inability to lie flat
6. Weight greater than 200 kg (too large for CT scanner)

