9.4.2 CT Image Acquisition Protocol (applicable to fixed site and mobile CT)

Preparation

Participants' weight and height will be ascertained prior to scanning to permit selection of exposure factors.

Subject Position: Participants should lie supine on the CT table with arms above their head and thorax in the midline of the scanner. Subject comfort should be optimised and maximal inspiration rehearsed prior to the scan to minimise motion during the CT. Imaging should be performed during suspended maximal inspiration. No intravenous contrast material will be administered.

Localiser: Sites should use their standard scanogram to localise the start and end positions of the scan. The frontal localiser should be performed in the PA projection

(tube at gantry bottom, patient supine) and at the lowest possible setting (e.g., 80 kVp, 20 mAs) to minimise breast dose.

Volumetric CT scan: The lung parenchyma (lung apices to bases) must be scanned in its entirety in a single craniocaudal acquisition. The field of view (FOV) selected as the smallest diameter as measured from widest point of outer rib to outer rib large enough to accommodate the entire lung parenchyma (usually no more than 35cm). Thin detector collimation (0.5 – 0.625mm) will be used with a pitch of 0.9-1.1. Scan time should usually be in the region of 5 seconds but must not exceed 10 seconds to avoid respiratory motion artefact. Sufficient delay time must be given after completion of the inspiratory command to ensure inspiration is complete prior to scan commencement. A start delay of 5-7s is usually appropriate, during which breathing commands are given.

Exposure factors: Radiation exposures will be as low as possible whilst maintaining good image quality. The CT dose index (CTDIvol) will be kept below 4 mGy, with the effective radiation dose well below 2 mSv. The kVp and mAs settings will be varied according to participant body habitus:

	Slim subjects (<50 kg BW)	Standard (50-90 kg BW)	Large (>90 kg BW)
kVp setting	100 kVp	120 kVp	140 kVp
mAs settings*	*depending on scanner type adjusted to achieve CTDI given below		
CTDIvol	0.8 mGy	1.6 mGy	3.2 mGy
Effective dose	<0.5 mSv	<0.8 mSv	<1.4 mSv
Effective dose including scout view (0.2mSv)	<0.7 mSv	<1.0mSv	<1.6mSv

If available, adaptive filtering should be used to optimise image quality, especially in the shoulder region and lung apices. Dose modulation packages should be used according to local practice.

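### The consent statement that the dose will nearly always be under 1 mSv has no weight condition, but the exposure table supports it only up to 90 kg

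*Protocol*

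**What the plan says.** Protocol section 4.4.1, item 3, deals with radiation risk. It begins with a general figure: "The amount of radiation delivered by one low dose CT scan of the chest to a standard-sized adult is approximately 1 mSv". A few sentences later it speaks of this trial: "In the UKLS protocol the radiation dose will almost invariably be less than 1 mSv". The item closes by committing to explain all of this to every potential participant at consent.

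Section 9.4.2 sets the exposures. Its overall requirement is a CTDIvol under 4 mGy, "with the effective radiation dose well below 2 mSv". A table then gives three weight bands, with mAs "depending on scanner type adjusted to achieve CTDI given below":

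| | Under 50 kg | 50-90 kg | Above 90 kg |
|---|---|---|---|
| CTDIvol (mGy) | 0.8 | 1.6 | 3.2 |
| Effective dose, scan only (mSv) | <0.5 | <0.8 | <1.4 |
| Effective dose with scout (mSv) | <0.7 | <1.0 | <1.6 |

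The heaviest band is headed "Large (>90 kg BW" and the last row "Effective dose including scout view (0.2mSv". Section 7.2 excludes on weight only at "Weight greater than 200 kg (too large for CT scanner", so people between 90 and 200 kg can enter.

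**The concern.** Item 3 applies one dose figure to everyone, while section 9.4.2 plans the dose by weight. For someone above 90 kg, the higher setting is the routine one for their size and not an occasional departure. The general sentence in item 3 is limited to an adult of standard size, but the sentence about this trial carries no such limit. A heavier person told only what item 3 says would hear a figure below the protocol's own limit for them.

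What is at stake is the accuracy of risk information promised at consent. Item 3 itself records the view that no radiation dose is free of harm, so the protocol treats dose as something to disclose correctly. The trial's endpoints, sample size and analysis are not touched.

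**Working it through.** **Inputs.** The claim of under 1 mSv and the conversion of 1 mSv to about 5 months of natural background come from section 4.4.1, item 3. The scan limits, CTDIvol targets and 0.2 mSv scout dose come from the table in section 9.4.2. The comparison is for one scan.

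**Step 1: reproduce the table's totals.** Limit with scout = scan limit + 0.2 mSv.

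- Under 50 kg: 0.5 + 0.2 = 0.7 mSv
- 50-90 kg: 0.8 + 0.2 = 1.0 mSv
- Above 90 kg: 1.4 + 0.2 = 1.6 mSv

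All three match the table.

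**Step 2: compare with 1 mSv.** The first two bands have limits at or below 1 mSv and support item 3. The third does not, whether the scout is counted (1.6 mSv) or left out (1.4 mSv). The overall requirement in section 9.4.2 does not help, because it refers to 2 mSv; a limit of 1.6 mSv is consistent with it.

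**Step 3: size of the gap.** At the table's limit the difference is 1.6 - 1.0 = 0.6 mSv. By item 3's conversion this is 0.6 x 5 = 3 months of background radiation.

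**Step 4: what it takes to stay under 1 mSv above 90 kg.** The CTDIvol target doubles, from 1.6 to 3.2 mGy.

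- With the scout, the scan itself must stay below 1.0 - 0.2 = 0.8 mSv. That is 0.8 / 1.4 = 57% of its limit, or 0.8 / 3.2 = 0.25 mSv per mGy.
- Without the scout, it must stay below 1.0 mSv. That is 1.0 / 1.4 = 71% of its limit, or 1.0 / 3.2 = 0.3125 mSv per mGy.

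The band's own limit corresponds to 1.4 / 3.2 = 0.4375 mSv per mGy. This is a ceiling divided by a target, not a measured conversion factor. It shows that the plan allows a dose above 1 mSv; it does not say how often one would occur.

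**The case against.** The strongest reply is that item 3 makes a statement of frequency for the whole trial, and its wording already allows exceptions. To show it wrong one would need the share of participants above 90 kg and the doses they receive, and the protocol gives neither. The dose entries in the table are upper limits, and section 9.4.2 asks for exposures as low as image quality permits and adds: "Dose modulation packages should be used according to local practice". Doses below 1 mSv above 90 kg are therefore compatible with the table. The participant information is not at hand and may already give doses by weight.

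Much of this stands, and it rules out three stronger readings that a reader might infer:

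- **That the sentence is false for the trial as a whole.** This cannot be shown without the weight distribution.
- **That scans above 90 kg will exceed 1 mSv, or will do so in most cases.** The table bounds the dose from above only. The implied ceilings per mGy fall as weight rises (0.5 / 0.8 = 0.625; 0.8 / 1.6 = 0.50; 1.4 / 3.2 = 0.4375), so they do not reveal the true conversion in the heaviest band.
- **That the quoted cancer risk of 1 in 20,000 is too low for heavier people.** The dose behind that figure is not given, and it may already cover them.

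What does not stand is the idea that the hedge settles the matter. A weight band set in advance, with its own tube voltage and CTDIvol target, is not a rare exception for the people in it. Item 3 does not tell them that their limit differs. Dose modulation left to local practice also guarantees no particular reduction.

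**Conclusion.** The point holds as a minor inconsistency between consent-facing risk wording and the protocol's own exposure table. Item 3's figure is backed by the table's limits up to 90 kg. Above 90 kg the dose may exceed 1 mSv, by at most 0.6 mSv per scan with the scout if the table's limits are kept. All three bands remain within the overall requirement of section 9.4.2.

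The conclusion rests only on figures printed in the protocol and needs no assumption about how many participants weigh more than 90 kg. Whether the participant materials repeat the sentence is unknown, so an effect on what participants actually read is possible but not established.

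**What to change.** In section 4.4.1, item 3, replace the sentence about the trial's dose with the single-scan limits from section 9.4.2, scout view included: below 0.7 mSv under 50 kg, below 1.0 mSv at 50-90 kg, and below 1.6 mSv above 90 kg. Use the same figures in the participant information if it repeats the sentence. Leave the 1 in 20,000 figure as it is, because the protocol does not give the dose on which it is based.

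The cost is a wording amendment. Its one drawback is that the stated dose becomes less favourable for participants above 90 kg.
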